Statistical Methods	The primary endpoint for measuring anti-tumor activity will be ORR, based on RECIST 1.1, which will be summarized as the overall number (%) of participants with CR or PR in each treatment arm, along with 95% confidence interval (CI). Participants will be analyzed based on the treatment arm to which they were randomized, as well as by lerapolturev dose/schedule (ie, QW and Q3/4W). Other endpoints will be summarized by descriptive statistics, as appropriate. Further details for these and other analyses will be described in the statistical analysis plan (SAP).
Determination of Sample Size	Sample size was determined based on feasibility and logistical considerations. Based on an estimated sample size of 15 participants in Arm 2 receiving lerapolturev QW in combination with anti-PD-1, five objective responses are needed for the 95% confidence interval (CI) to be above 10% (33% ORR; 95% CI: 11.8% to 61.6%), which would indicate the combination has antitumor activity in this anti-PD-1 resistant population. See Section 8.3 for additional details regarding sample size determination.
Study Duration	Up to approximately 24 months (104 weeks)

Confidential Page 18 of 109

^Criteria for Crossover

- radiologic disease progression per RECIST v1.1 (progression does not need to be confirmed prior to crossover)
- has not had progression or confirmed partial response per RECIST v1.1 by week 26 on study
- partial response ≥ 6 months in duration

Confidential Page 19 of 109

Table 1. Schedule of Assessments for Lerapolturev Monotherapy or Lerapolturev + Pembrolizumab

NOTE: Cycle length for lerapolturev monotherapy or lerapolturev + pembrolizumab is 3 weeks. Lerapolturev is administered weekly during Cycles 1 & 2 and every 3 weeks thereafter on the days indicated in the table below. Refer to the table below for the timing of other study assessments to be completed within each cycle.

	Screening Period	o		EOT Visit ¹⁵	Survival Follow- up ¹⁶	
Study Procedure ³		Cycle 1	Cycle 2	≥ Cycle 3		
	(≤ 28D prior to C1D1)		+3W (+7D)	Q3W (+7D)	≤28D after last treatment	
Informed Consent ¹	X					
Medical History	X					
Physical Exam ^{2,3}	X	C1D1	C2D1	Day 1 of each Cycle	X	
Vital Signs ³	Х	C1D1, C1D8, C1D15	C2D1, C2D8, C2D15	Day 1 of each Cycle	X	
ECOG Performance Status ³	Х	C1D1	C2D1	Day 1 of each Cycle	Х	
PV Immunization Booster ¹	≥1W, but ≤6W before C1D1					
Adverse Events		Conti	Continuous from signing ICF until 30 days after last dose of study therapy			

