6.3 Participant Withdrawal from the Trial

Participants may be withdrawn from the study under any of the following circumstances:

- Withdrawal of consent
- Lost to follow-up
- Administrative reasons (eg, Sponsor decision)
- Major violation of the protocol
- If in the opinion of the investigator, it is in the best interest of the participant
- Non-compliance
- Termination of the study

Participant follow-up should continue as specified in the protocol until the scheduled date of study completion, or until recovery or stabilization of an AE, whichever comes last. All

Confidential Page 71 of 109

participants that permanently discontinue study treatment should be followed for survival and disease progression outcomes; these assessments may be made via telephone contact if local follow-up is not possible. At minimum, all participants should have an EOT visit that includes tumor measurements (imaging and cutaneous measurements) and a focused physical assessment prior to study withdrawal. Chemistry and hematology should be collected, if possible. Investigators should also provide a final and best overall anti-tumor response assessment with the eCRF.

Lost to Follow-up

A participant will be considered lost to follow-up if they fail to return for 2 scheduled visits and are unable to be contacted by the study site. The following actions must be taken if a participant fails to return to the clinic for a required study visit:

- The site must attempt to contact the participant, reschedule the missed visit as soon as possible, counsel the participant on the importance of maintaining the assigned visit schedule, and ascertain whether the participant wishes to and/or should continue in the study.
- Before a participant is deemed lost to follow-up, the investigator or designee
 must make every effort to regain contact with the participant (where possible,
 3 telephone calls and, if necessary, a certified letter to the participant's last
 known mailing address or local equivalent methods). These contact attempts
 should be documented in the participant's medical record.
- Should the participant continue to be unreachable, they will be considered to have withdrawn from the study.

Participants who are lost to follow-up may be replaced at the Sponsor's discretion.

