8.4 Populations for Analyses

For participants receiving the **QW** schedule of lerapolturev injections, enrollment will be stratified based on baseline LDH levels (normal versus >ULN) and type of anti-PD-1/L1 resistance (primary versus secondary), primarily for the purpose of balancing key participant descriptors between the treatment arms. For purposes of analysis, the following key populations are defined; additional populations may be defined in the SAP:

Population	Description
Intent-to-treat	All participants who sign the ICF and are randomized
Efficacy QW Schedule	Participants receiving at least one lerapolturev injection on the QW schedule and at least 1 post-baseline evaluation
Efficacy—Q3/4W Schedule	Participants receiving at least one lerapolturev injection on the Q3/4W schedule and at least 1 post-baseline evaluation
Crossover	Participants from Arm 1 receiving at least one lerapolturev injection with concurrent anti-PD-1 and at least 1 post-crossover evaluation
Safety—QW	Participants receiving at least one lerapolturev injection on the
Schedule	QW schedule
Safety—Q3/4W	Participants receiving at least one lerapolturev injection on the
Schedule	Q3/4W schedule

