4.2. EFFICACY

Participants receiving at least one lerapolturev injection and at least 1 post-baseline assessment. If a participant crosses over from monotherapy to combination therapy, then the treatment analyzed will be based on the treatment for that participant at the time of the assessment for the efficacy set.

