5.6.1.1. Statement of Estimand

The **population for the trial** is defined through appropriate inclusion/exclusion criteria to reflect the targeted participant population for approval. The analysis population is based on the efficacy population.

The **treatments** of interest are lerapolturev alone or lerapolturev + an FDA-approved anti-PD-1 therapy by dosing schedule.

The **variable** of interest for ORR is the binary response value for a participant.

The ability to evaluate treatment effect using the variables may be impacted by **intercurrent events** (ICEs). Death and use of additional cancer treatments may all impact the interpretation of treatment effect. For ORR, a composite strategy will be used to address intercurrent events (ICEs) of potential death, and start of additional cancer treatments, meaning occurrence of any of these events prior to a participant achieving CR or PR will mean the participant is considered a non-responder.

The **population level summary measures** are the ORR and associated confidence intervals in each treatment arm and lerapolturev dosing schedule.

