10. PROGRAMMING CONVENTIONS

- Page orientation, margins, and fonts: Summary tables, listings, and figures will appear in landscape orientation. There should be a minimum of a 1.0" boundary on the left and right edges. The top and bottom margins are 1.0" for tables and listings but may vary for figures. Output should be printed in Courier New with a point size of 8. Titles may be printed using a larger font (eg, Arial point size 10).
- Identification of analysis population: Every summary table and figure should clearly specify the analysis population being summarized. Listings will be prepared for all participants.
- Group headers: In the summary tables, the group headers will identify the summary group and the sample size for the indicated analysis population. Of note, the header's sample size does not necessarily equal the number of participants summarized within any given summary module; some participants in the analysis population may have missing values and thus may not be summarized.
- Suppression of percentages corresponding to null categories: When count data are presented as category frequencies and corresponding percentages, the percent should be suppressed when the count is zero to draw attention to the non-zero counts.
- Presentation of sample sizes: Summary modules should indicate, in one way or another, the number of participants contributing to the summary statistics presented in any given summary module. As mentioned above, this may be less than the number of participants in the analysis population due to missing data.
 - In the quantitative modules describing continuous variables (and thus presenting sample size, means, and standard deviations), the sample size should be the number of non-missing observations. The number of missing observations, if any, will be noted.
 - For categorical variables that are presented in frequency tables, the module should present the total count in addition to the count in each category. Percentages should be calculated using this total as the denominator, and the percentage corresponding to the sum itself (that is, 100%) should be presented to indicate clearly to a reviewer the method of calculation. The number of missing observations, if any, will be noted.
- Sorting: Listings will be sorted by treatment group, participant number and date, if applicable. If a listing is sorted in a different manner, a footnote will indicate as such.

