11. PROPOSED TABLES, LISTINGS, AND FIGURES

Summary Tables

Accountability and Baseline Characteristics		
14.1.1.1	Participant Disposition, Screening Analysis Set	
14.1.2.1	Demographics and Baseline Characteristics, Safety Set	
14.1.4.1	Melanoma History, Safety Set	
14.1.4.2	Biomarker History, Safety Set	
14.1.4.3	Prior Systemic and Intratumoral Anti-Cancer Therapy, Safety Set	
14.1.4.4	Prior Radiotherapy for Melanoma, Safety Set	
14.1.4.5	Prior Procedures, Safety Set	
14.1.4.6	Concomitant Medications, Safety Set	
14.1.4.7	Concomitant Procedures, Safety Set	
14.1.4.8	Subsequent Anti-Melanoma Treatment, Safety Set	
14.1.5.1	Summary of Study Drug Exposure, Safety Set	
Efficacy		
14.2.1.1	Summary of Best Overall Tumor Response Based on RECIST 1.1 Criteria,	
	Efficacy Set	
14.2.2.1	Summary of Overall Survival, Efficacy Set	
14.2.3.1	Summary of Progression Free Survival, Efficacy Set	
Safety		
14.3.1.1	Overall Summary of Treatment-Emergent Adverse Events, Safety Set	
14.3.1.2	Treatment-Emergent Adverse Events by System Organ Class, Preferred Term, and	
14.5.1.2	Greatest Severity, Safety Set	
14.3.1.3	Treatment-Emergent Adverse Events by Preferred Term in Descending Frequency,	
17.3.1.3	Safety Set	
14.3.1.4.1	Treatment-Emergent Adverse Events Related to Lerapolturev by System Organ	
1	Class, Preferred Term, and Greatest Severity, Safety Set	
14.3.1.4.2	Treatment-Emergent Adverse Events Related to Anti-PD-1 by System Organ	
	Class, Preferred Term, and Greatest Severity, Safety Set	
14.3.1.5.1	Treatment-Emergent Adverse Events Related to Lerapolturev by Preferred Term in	
	Descending Frequency, Safety Set	
14.3.1.5.2	Treatment-Emergent Adverse Events Related to Anti-PD-1 by Preferred Term in	
	Descending Frequency, Safety Set	
14.3.2.1	Treatment-Emergent Serious Adverse Events by System Organ Class, Preferred	
	Term, and Greatest Severity, Safety Set	
14.3.2.2.1	Treatment-Emergent Serious Adverse Events Related to Lerapolturev by System	
	Organ Class, Preferred Term, and Greatest Severity, Safety Set	
14.3.2.2.2	Treatment-Emergent Serious Adverse Events Related to Anti-PD-1 by System	
	Organ Class, Preferred Term, and Greatest Severity, Safety Set	
14.3.3.1	Treatment-Emergent Lerapolturev Adverse Event of Special Interest by System	
	Organ Class, Preferred Term, and Greatest Severity, Safety Set	
14.3.3.2	Treatment-Emergent Immune Related Adverse Event by System Organ Class,	
	Preferred Term, and Greatest Severity, Safety Set	

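### The Efficacy Set drops treated participants lost before any post-baseline assessment, which contradicts the ORR estimand's composite rule and can only raise the ORR and its lower confidence limit

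*SAP*

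**What the plan says.** SAP 4.2 limits the Efficacy Set to "Participants receiving at least one lerapolturev injection and at least 1 post-baseline assessment". Protocol 8.4 has the same restriction for the weekly (QW) schedule: "Participants receiving at least one lerapolturev injection on the QW schedule and at least 1 post-baseline evaluation". Neither document says whether a caliper measurement, a scan or any visit satisfies the condition.

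For the primary endpoint, SAP 5.6.1.1 states that "The analysis population is based on the efficacy population". The same section applies a composite strategy to death and to the start of additional cancer treatment: "occurrence of any of these events prior to a participant achieving CR or PR will mean the participant is considered a non-responder".

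In SAP 11, every efficacy table and figure (best overall response, OS, PFS, and the DOR, OS and PFS curves) carries the Efficacy Set label, for example "Summary of Overall Survival, Efficacy Set". SAP 4.1 defines an ITT set and SAP 4.3 an all-treated Safety Set, but no listed efficacy table or figure uses either one.

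The decision rule (Protocol 8.3, SAP 3.1) is that the QW combination is considered active if the lower 95% confidence limit for ORR exceeds 10%. The plan gives 5 of 15 responders as the minimum.

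**The concern.** The composite rule exists so that a participant who dies or moves to another therapy before responding counts against the treatment. It can act only on people in the analysis set. Someone with that event before any post-baseline assessment is removed first, so the two rules contradict each other and the set definition prevails.

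The selection runs one way. A participant with no post-baseline assessment cannot have a confirmed response, so everyone removed is a non-responder. The ORR and its lower limit, on which the only decision rule rests, can rise but not fall.

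For OS the restriction has no purpose. SAP 3.2.6 runs OS from start of treatment to death from any cause, and Protocol 7.1 collects survival status without needing a tumour measurement. The condition deletes the earliest deaths from OS, and from PFS, where death is also an event.

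**Working it through.** **Inputs.** Planned QW combination arm n = 15, threshold 10%, exact two-sided 95% Clopper-Pearson interval (SAP 3.1, 5.6.1.2). The documents give no unevaluable rate, so the rate d is an assumption, varied from 0 to 25%.

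**Step 1: reproduce the plan's figure.** For x responders of n, the lower limit is the 2.5% quantile of Beta(x, n − x + 1). 5/15 gives 11.8% (interval 11.8% to 61.6%) and 4/15 gives 7.8%. The stated minimum of 5 and its interval both reproduce.

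**Step 2: 15 treated, some excluded.**

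| All treated | Excluded | Efficacy Set | ORR shown | Lower limit | Decision |
|---|---|---|---|---|---|
| 5/15 | 0 | 5/15 | 33.3% | 11.8% | pass |
| 5/15 | 1 | 5/14 | 35.7% | 12.8% | pass, unchanged |
| 5/15 | 2 | 5/13 | 38.5% | 13.9% | pass, unchanged |
| 4/15 | 3 | 4/12 | 33.3% | 9.9% | fail, unchanged |
| 4/15 | 4 | 4/11 | 36.4% | 10.9% | fail becomes pass |

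**Step 3: more than 15 treated.** 5/16 gives 11.0%, 5/17 gives 10.3% and 5/18 gives 9.7%. One exclusion changes the decision if 18 are treated (5/18 fails, 5/17 passes). If 15 evaluable participants come from 18 treated, 5/15 passes where 5/18 would fail. Both cases need an arm larger than planned.

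**Step 4: chance of declaring activity.** Let each treated participant respond with probability p and be unassessed with probability d, never both. Among the assessed, the response probability is p/(1 − d). Let r(n) be the smallest count with a lower limit above 10%: r = 4 for n = 9 to 11, 5 for 12 to 17, and 6 for 18 to 21. For N treated, the chance is the sum over m of Bin(m; N, d) × P[Bin(N − m, p/(1 − d)) ≥ r(N − m)].

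With N = 15 and d = 10%, the chance at a true ORR of 10% goes from 1.27% to 1.39%; at a true ORR of 15% it goes from 6.2% to 6.5%. The change is small because r stays at 5 from n = 12 to 17, so losing one to three of 15 does not lower the count needed.

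Across the assumed range, at a true ORR of 10%:

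| Assumed d | 15 treated | 15 evaluable, extra enrolled |
|---|---|---|
| 0% | 1.3% | 1.3% |
| 10% | 1.4% | 2.0% |
| 20% | 2.2% | 3.1% |
| 25% | 2.9% | 4.0% |

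The 2.5% lower tail of the interval is passed only between 20% and 25% unevaluable in the first column, and above about 15% in the second.

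**The case against.** The best case for the plan is that few people would be excluded. Calipers are scheduled from Cycle 1 Day 8, so if those count, only first-week losses leave the set. If imaging is required, the first scan is at week 6, but Protocol 6.3 asks for an end-of-treatment visit with tumour measurements from anyone who leaves. Eligibility requires ECOG 0–1 and life expectancy above 12 weeks, and excludes M1c and M1d disease. Zero or one exclusion in 15 is plausible. This stands as to size. It does not remove the contradiction: a participant who dies early has no such visit, and the outcome depends on a term left undefined.

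Several stronger readings are tempting, and the documents do not support them:

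- *All early deaths and drop-outs leave the denominator.* Only those before any post-baseline assessment do.
- *Percentages ignore non-evaluable participants.* SAP 10 says "Percentages should be calculated using this total as the denominator", but SAP 5.6.1.2 lists non-evaluable as a best-response category, so those in the set are counted in the total.
- *The SAP departs from the protocol.* Protocol 8.4 has the same restriction. The synopsis sentence "Participants will be analyzed based on the treatment arm to which they were randomized" concerns grouping by arm, not who is counted.
- *Replacement causes the bias.* Protocol 6.3 says "Participants who are lost to follow-up may be replaced", at the sponsor's discretion. That removes no one from the set; it only makes an arm above 15 possible.
- *The decision is easily flipped.* One could take the ceiling of about 50 randomised, subtract the 12 already randomised on the Q3/4W schedule and halve: (50 − 12)/2 = 19. With 10% unevaluable at n = 19, the chance of declaring activity rises from 0.9% to 2.1% at a true ORR of 10%, and from 5.4% to 9.9% at 15%. But the plan states 15, and 30 + 12 = 42 fits under the ceiling. The 2.1% is still below 2.5%, and at a true ORR of 15% a declaration is not a false positive.
- *All survival curves are materially biased.* A participant lost early while alive would be censored early and hardly moves the curve; only very early deaths matter.

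**Conclusion.** The point holds as an internal contradiction with a one-directional effect. SAP 4.2 removes participants whom SAP 5.6.1.1 intends to count as non-responders, and it deletes the earliest deaths from OS and PFS. What rises is the observed ORR and its lower limit; the 10% threshold is fixed.

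At the planned 15 treated, one or two exclusions raise a 5-responder lower limit by about 1 to 2 percentage points without changing the decision. A 4-responder result needs four exclusions to pass. A reader might infer that the decision rule is seriously compromised. At the planned size that would take an unevaluable rate for which the documents give no basis. These figures assume that every excluded participant is a non-responder, which follows from the definitions, and that d lies between 0 and 25%, which is an assumption. This is a should-fix point.

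**What to change.** In SAP 4.2, 5.6 and the SAP 11 table list:

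- Run ORR, DCR, DCR-6mo, DRR, OS and PFS on all treated participants (Safety Set), and on ITT as assigned for the randomised arms. Keep the existing rule that monotherapy response is taken before crossover.
- Count participants without a post-baseline assessment as non-responders, with the response-rate denominators fixed at the size of the set.
- Keep the Efficacy Set as a supportive analysis and define the post-baseline assessment it requires.
- Report the ORR confidence limits to one decimal. SAP 10 prints calculated percentages without decimals; applied to confidence limits, that would show both 9.7% and 10.3% as 10%.

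The cost is SAP wording, population labels and some repeated tables. No extra data are needed. The reported ORR may be slightly less favourable.

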4.3. SAFETY

Participants receiving at least one lerapolturev injection. If a participant crosses over from monotherapy to combination therapy, then the treatment analyzed will be based on the treatment for that participant at the time of the assessment.

